11.4 ANALYSIS POPULATIONS

The **randomized population** will include any patient who had been allocated to a randomized treatment arm regardless if study drug was administered.

The **safety population** is a subset of the randomized population and will include randomized patients who received at least 1 infusion (partial or total). This is the primary population for the safety analysis.

The **mITT population** is the same as the safety population, and is used as the primary population for the efficacy analysis.

The **per protocol** population will be a subset of the mITT population who have no major protocol deviations that are expected to interfere with assessments of the 2 primary efficacy endpoints.

The **extension treatment population** will consist of patients who completed the PAP and who continue into the extension treatment period.

The **PK population** will consist of mITT patients who have evaluable drug concentration data.

The **PD population** will consist of mITT patients who have at least 1 evaluable PD marker data available post-baseline.

Patients who are included in the safety population and have rescue therapy initiated are included in the **rescue therapy population**. Since in the ETP all subjects get olipudase alfa, the rescue therapy is relevant only for the PAP.

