11.5.2.1 Primary efficacy analysis

The 2 primary efficacy endpoints (percentage change in spleen volume in MN from baseline to Week 52 [combined with change in SRS from baseline to Week 52 in the US only, and is referred to as the “combination spleen endpoint”]) and percentage change in DL_{CO} in percent predicted from baseline to 52 weeks) will be analyzed in the mITT population using the mixed model for repeated measures.

For percent change in DL_{CO} (% predicted) from baseline, the mixed model for repeated measures (MMRM) will include baseline DL_{CO} (% predicted), baseline age, treatment arm, study visit (Week 26, Week 52), and study visit by treatment arm interaction as covariates; have an unstructured variance-covariance matrix; and be fit using restricted maximum likelihood estimation. Comparisons between treatment arms will be made using least-square mean contrasts at the 52 week visit.

The analysis will include all DL_{CO} observations after baseline in the first 12 months of the study regardless of the treatment discontinuation status, with the exception that measurements made after the switch of treatment (eg, placebo patients switch to olipudase alfa after meeting the rescue criteria) will not be considered. For the primary analysis, missing data will not be imputed and will be assumed as Missing at Random (MAR).

Similar analyses will be performed for the spleen volume (MN) and the splenomegaly-related symptom score (SRS), when baseline value of the spleen volume (or SRS) will be used as covariate.

Descriptive assessment of MAR assumption and sensitivity analyses to assess the impact of missing data are described in the SAP.

Hypothesis tests will be 2-sided and adjusted for multiple comparisons to maintain a family-wise Type 1 error rate of 5%. The details of multiplicity adjustments are provided in [Section 11.5.4](#).

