### 1.1 STUDY DESIGN AND RANDOMIZATION

This Phase 2/3, multicenter, repeat-dose, clinical trial will be divided into 2 consecutive major periods: 1) a randomized placebo-controlled, double-blind PAP from Day -60 to Week 52 to be followed by 2) an ETP. Initially, the ETP will be double-blind as patients in the placebo arm cross over to active treatment. Study drug will be defined during the PAP as olipudase alfa or placebo, and during the ETP as olipudase alfa, and will be administered intravenously once every 2 weeks for 52 weeks in PAP, then for ETP. Day -60 to -1 is part of screening period with no study drug; some of the screening assessments which are not repeated right before the first infusion of study drug on Day 1 serve as baseline value for the study.

After completing the PAP, patients will enter the ETP of the study. Those who were randomized to the active arm will continue receiving the dose they were receiving at the completion of the PAP. Patients randomized to the placebo arm in the PAP will cross over to active treatment in the first infusion in ETP and will undergo dose escalation to a target dose of 3.0 mg/kg olipudase alfa.

For treatment periods during the PAP and the ETP, dose-limiting toxicity (DLT) criteria (protocol Section 8.1.4) and study stopping rules (protocol Section 8.1.5) will apply. If a patient satisfies protocol-specified criteria of rescue therapy (protocol Section 8.1.6), the individual treatment blind will be broken and the patient if on placebo will be switched to olipudase alfa; for patients already on olipudase alfa, the treatment will continue unless the patient drops out of study.

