## 1.4 STUDY PLAN

This Phase 2/3, multicenter, repeat-dose, clinical trial will be divided into 2 consecutive major periods: 1) a randomized placebo-controlled, double-blind PAP from Day -60 to Week 52, to be followed by 2) ETP for up to 4 years. Initially, the ETP will be double-blind as patients in the placebo arm cross over to active treatment, and the last patient completes PAP and when this patient is going through dose escalation the study is unblinded for analysis of PAP; ETP after unblinding for PAP analysis is open-label where all patients receive olipudase alfa.

The PAP will include a screening/baseline period and a treatment period. Approximately 36 patients who meet the eligibility criteria will be randomized in a 1:1 ratio across sites into 1 of 2 arms, placebo or 3.0 mg/kg olipudase alfa target dose. Patients will undergo a dose-escalation period to achieve the target dose level.

After completing the PAP, patients will enter the ETP. Patients randomized to the placebo arm in the PAP will cross over to active treatment in the ETP and will undergo dose escalation to a target dose of 3.0 mg/kg olipudase alfa. The patients who were randomized to the active arm will continue receiving olipudase alfa at the dose they complete PAP (with a mock dose escalation period to maintain blinding).

Study drug will be administered intravenously once every 2 weeks. In-patient hospitalization is required during dose escalation period and specific visits. Other infusions are administered at the clinic.

All patients will have an end of study/early discontinuation visit within 2 weeks after the last infusion of study treatment. In addition, all patients will receive a follow-up phone call for safety approximately 30 to 37 days after the last infusion of study drug.

A rescue strategy for patients who experience significant clinical decline (specific guidelines in the protocol, Section 8.1.6) will be in place: these individual patients may be unblinded and if receiving placebo, will be switched to olipudase alfa with proper dose escalation to a target dose of 3.0 mg/kg. These patients will continue to be followed to the end of study.

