## 1.5 MODIFICATIONS TO THE STATISTICAL SECTION OF THE PROTOCOL

This section summarizes discrepancies between the statistical analysis described in the amended DFI12712 protocol 11, dated 12 August 2019, and this SAP.

- The following language about the summary of immune response assessments in the protocol Section 11.5.5.4 will not be provided by the dose level of the infusion before or during the evaluation, since the infusion information will be included in the data listing.  
*The presence, absence, and titers of serum anti-olipudase alfa IgG antibodies and routine levels of acute phase reactants will be summarized over time overall and by the dose level of the infusion before or during the evaluation.*
- The following language about the exploratory pharmacodynamic analyses in the protocol Section 11.5.6.2 is not planned in this SAP but may be done ad hoc if deemed necessary.  
*Exploratory correlation analyses will be attempted to evaluate relationships between different PD markers and between sphingomyelin and /or lysosphingomyelin levels from different sources.*
- Multiplex assay of inflammatory and vascular biomarkers are analyzed as both exploratory efficacy and safety endpoints in the protocol but will be treated only as safety endpoints in this SAP.
- The ETP population mentioned in the protocol Section 11.4 was removed from the SAP, since data for PAP+ETP will be analyzed in a cumulative way.
- The annualized rate of TEAEs and separate analyses of AEs by demographic characteristics (eg, age and sex) mentioned in the protocol Section 11.5.5.1 will be presented in the integrated summary of safety and will not be done in the study SAP.

- Protocol Section 11.5.6.3 for pharmacokinetic-pharmacodynamic analyses will not be done at the study level, but may be conducted using pooled data from different clinical studies and the results may be included in a separate report.
- For the summary of exposure, the protocol mentioned using the safety population. However, the population was changed to mITT population in the SAP in order to accurately summarize the duration of exposure prior to rescue therapy for patients who were randomized to placebo at the beginning.

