### **2.3.2 Safety population**

The **safety population** is defined as a subset of the randomized population who received at least 1 infusion (partial or total), analyzed according to the treatment actually received during the PAP, irrespective of the treatment to which the patient has been randomized. For example, if a placebo patient was rescued to receive olipudase alfa in PAP, this patient will be counted as olipudase alfa treated patient. The safety population will not be changed after patients enter the ETP. Olipudase alfa infusions require special vials to be mixed with the vehicle while placebo infusions do not require these vials, and these vial numbers are called off by IXRS, it is unlikely that there will be any error in treatment received.

The **rescue population** is defined as patients who have used rescue strategy in PAP (ie, unblinded for treatment and continued on olipudase alfa irrespective of the randomized treatment assignment). Data after rescue in PAP will be provided separately for the rescue population.

In addition, nonrandomized but treated patients will not be part of the safety population; however, their safety data will be presented separately.

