## **2.4.5 Analyses of efficacy endpoints**

Efficacy data will be analyzed by randomized treatment group in mITT population at scheduled time point. The statistical analyses will compare olipudase alfa versus placebo within PAP; the difference between two treatment groups is calculated as olipudase alfa minus placebo.

Primary analyses period is 52 weeks.

Efficacy analyses will use mITT population unless specified otherwise. This will include patients who used rescue therapy, but their data after rescue will NOT be included in the analysis. Sensitivity analyses including data beyond rescue therapy may be undertaken if appropriate.

Baseline values are generally the latest value before the first infusion of the study drug, except for platelets and hemoglobin which are part of hematology parameters; for hematology parameter baseline definition, please refer to [Section 2.6.1](#).

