The MMRM assumes data missing-at-random (MAR) and will include all DLco observations except for measurements made after the initiation of rescue therapy. In addition, for patients who do not have Week 52 value available but have a PFT value measured after Week 38 infusion (eg, patients discontinuing the study or initiating rescue therapy after Week 38 but before Week 52 may have the PFT measurements available from early discontinuation visit or right before rescue therapy starts), these values will be used as Week 52 value for analysis purposes; Week 52 DLco will not be considered missing in such situations. This idea is based on the clinical concept that PFT measurements are similar within a 12-week period.

The percentage change in spleen volume (MN) and the change in the splenomegaly-related score (for US, SRS is part of primary endpoints) will be analyzed using an analogous MMRM model.

The summary plots of the LS means from the MMRM of the percentage change in DLco (% predicted), the percentage change in spleen volume (MN) and the change in the splenomegaly-related score from baseline up to Week 52 with 95% CIs will be provided.

Sensitivity analyses for the primary efficacy endpoints to support robustness of results will include the following:

1. The MMRM described above will be run using the per-protocol population. This analysis will demonstrate whether the results vary depending on the population analyzed.
2. The MMRM described above will exclude observations made after the initiation of rescue therapy. As a sensitivity analysis, the observations collected after the initiation of rescue therapy will be included in the MMRM; the treatment arm for rescued patients will remain

as randomized treatment.

The MMRM planned for the primary efficacy analysis assumes MAR. To assess the robustness of the primary results to that assumption a pattern mixture model will be used (see [Section 2.6.6](#) for details).

3. The MMRM planned for the primary efficacy analysis assumes multivariate normality. To assess the robustness of conclusions under this assumption, nonparametric testing method will be used: A Wilcoxon-Mann-Whitney (WMW) will be used to compare the primary efficacy endpoints; missing Week 52 data will be imputed using LOCF, excluding patients who initiate rescue therapy.

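### Read literally, the SAP drops post-rescue values of olipudase alfa patients that the protocol's primary analysis keeps, and SAP 1.5 does not list the difference

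*SAP*

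**What the plan says.** Protocol 11.5.2.1 keeps every post-baseline DLco value in the first 12 months, whether or not treatment was discontinued, with one exception: "measurements made after the switch of treatment (eg, placebo patients switch to olipudase alfa after meeting the rescue criteria) will not be considered". Spleen volume and SRS are handled similarly.

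The SAP words the exception differently. Section 2.4.5.1 says that the model "will include all DLco observations except for measurements made after the initiation of rescue therapy". Section 2.4.5 sets the general rule for the mITT efficacy analyses: "This will include patients who used rescue therapy, but their data after rescue will NOT be included in the analysis". The SAP does not define what initiating rescue therapy means.

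Three other places describe what rescue means for a patient already on active drug:

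- SAP 2.3.2 defines the rescue population as patients who used the rescue strategy in the PAP, that is, "unblinded for treatment and continued on olipudase alfa irrespective of the randomized treatment assignment".
- SAP 1.1 says that "for patients already on olipudase alfa, the treatment will continue unless the patient drops out of study".
- Protocol 8.1.6 says that any patient meeting a criterion (confirmed low hemoglobin, confirmed low platelets, or bleeding related to low platelets) is unblinded and moved to the 3.0 mg/kg group with escalation. It has no limit by arm. It also says that these patients stay in follow-up.

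SAP 1.5 exists to list differences from the protocol's statistical section. None of its seven items concerns the post-rescue exclusion in the efficacy analysis.

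**The concern.** The two rules have different triggers: a change of treatment in the protocol, and rescue in the SAP. They agree for a placebo patient, for whom rescue is a change of treatment. They part for an olipudase alfa patient who meets a criterion and carries on with the same drug. Two analysts working from the SAP could therefore build different primary datasets in a trial planned around 16 evaluable patients per arm.

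The affected values are not a random subset. They come from patients who have just met a criterion for clinical decline, and the literal rule replaces them with a missing-at-random assumption. For platelet count, second in the secondary hierarchy, the link is direct when platelets trigger the rescue. Entry requires at least 60 x 10^3/µL and rescue requires a confirmed value below 30 x 10^3/µL, so the fall is more than (60 - 30)/60 = 50%.

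**Working it through.** **Step 1. Apply each rule to the same patient.** Take a patient who meets a Protocol 8.1.6 criterion during the PAP and has a Week 52 measurement.

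| Randomized arm | Change of treatment? | Protocol 11.5.2.1 | SAP 2.4.5 and 2.4.5.1, literal |
|---|---|---|---|
| Placebo | Yes, to olipudase alfa | Week 52 dropped | Week 52 dropped |
| Olipudase alfa | No, continues (SAP 1.1) | Week 52 kept | Week 52 dropped (rescued under SAP 2.3.2) |

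Only the second row differs. Document versions do not explain it. Protocol Appendix C shows that the switch wording came in with amended protocol 09, before amended protocol 11, on which the SAP is based.

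**Step 2. Does a planned analysis reproduce the protocol rule?** Sensitivity analysis 2 in SAP 2.4.5.1 restores post-rescue values in both arms, with patients analysed as randomized. It therefore also puts on-drug values into the placebo arm, and it equals the protocol rule only if no placebo patient is rescued. One rescued placebo patient with a full response would lower the effect by up to 25/16 = 1.6 points (DLco) or 30/16 = 1.9 points (spleen volume). The Wilcoxon analysis excludes patients who initiate rescue, so the question of who counts as rescued arises there too.

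**Step 3. Inputs for size (SAP 1.3).** 36 patients randomized 1:1, with 11% not evaluable at Week 52: 18 x 0.89 = 16 per arm. Planned differences are 25 points (DLco, SD 20) and 30 points (spleen volume, SD 11.8). With 16 per arm, the two-sided 5% t-test for DLco has 92.8% power, against 93% stated, so this is the sample size behind the plan's own figure.

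**Step 4. Upper figure, per patient.** Assume a placebo mean change of zero, and one active-arm patient who ends at no change while the other 15 average the planned effect. With no earlier value to borrow from, removing the Week 52 value shifts the active mean by d52/16, where d52 is the patient's shortfall from the other patients' mean:

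- DLco: 25/16 = 1.56, about 1.6 points
- Spleen volume: 30/16 = 1.88, about 1.9 points

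Each is 1/16 = 6.25% of the planned effect. The standard errors are 20 x sqrt(2/16) = 7.07 and 11.8 x sqrt(2/16) = 4.17, so the shifts are 1.56/7.07 = 0.22 and 1.88/4.17 = 0.45 standard errors.

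**Step 5. With a Week 26 value kept.** The model borrows from Week 26, and the shift becomes (d52 - b x d26)/16. Here d26 is the shortfall at Week 26 and b is the within-arm slope of Week 52 on Week 26 (equal to the correlation if the two SDs are equal). The documents give neither d26 nor b, so both are assumed. If the kept value is already no change:

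- DLco, d26 = 15, b = 0.8: (25 - 12)/16 = 0.81. Over d26 = 12.5 to 20 and b = 0.5 to 0.8, the range is (25 - 16)/16 = 0.56 to (25 - 6.25)/16 = 1.17.
- Spleen volume, d26 = 20 to 25, b = 0.5 to 0.8: (30 - 20)/16 = 0.63 to (30 - 10)/16 = 1.25.

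Simulated fits of the planned model agreed closely: 0.5 to 1.2 for DLco and 0.6 to 1.2 for spleen volume. If the patient is still at the arm mean at Week 26, d26 is zero and the figures in Step 4 apply.

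**Step 6. Timing.** Protocol 8.1.6 requires MRI and PFTs at rescue if the last ones are more than 12 weeks old. SAP 2.6.4 lets an unscheduled efficacy value stand in for a missing 6- or 12-month value within 91 days.

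- Rescue before about Week 13 (Week 26 minus 91 days): no post-baseline value is kept, so Step 4 applies.
- Rescue from about Week 13 to Week 38: Step 5 applies.
- Rescue after Week 38: SAP 2.4.5.1 uses the rescue-time PFT as Week 52, and SAP 2.6.4 does much the same for spleen volume. Only the change after that test, divided by 16, is lost.

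**The case against.** The best answer is that the SAP means placebo patients only. SAP 1.4 says that "these individual patients may be unblinded and if receiving placebo, will be switched to olipudase alfa with proper dose escalation". SAP 1.5 justifies its exposure change by the need to summarize exposure "prior to rescue therapy for patients who were randomized to placebo at the beginning". SAP 2.4.4.1 computes exposure from a first rescue dose date, which a patient who merely continues does not have. Protocol 11.4 adds: "Since in the ETP all subjects get olipudase alfa, the rescue therapy is relevant only for the PAP". On that reading the two documents agree and SAP 1.5 had nothing to list. The arm-neutral definition in SAP 2.3.2 sits in the safety section and may serve only a separate display.

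The protocol side is not clean either. Its placebo example is only an example, and Protocol 8.1.6 speaks of switching any qualifying patient, which could be stretched to an active-arm patient who re-escalates.

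All of this stands as evidence of intent. It does not remove the conflict in the operative sentences, because the SAP's exclusion is unrestricted, its key term is undefined, and the only definition of a rescued patient covers both arms.

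A reader might infer that the SAP rule is biased toward olipudase alfa and raises the false-positive risk. The documents do not support that. The literal rule censors both arms at the same event, whereas the protocol rule drops decliners on placebo and keeps those on active drug. The shifts above are differences from the protocol rule and nothing more. A reader might also infer an intended, undisclosed departure from the protocol; the placebo-only wording above weighs against it. Finally, sensitivity analysis 2 is a useful conservative check, since it keeps active-arm decliners and credits rescued placebo patients' improvement to placebo. It is still not the protocol's primary rule.

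**Conclusion.** The point holds as a literal conflict between the SAP's primary data rule and the protocol's, not listed in SAP 1.5. It is not a proven intention.

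The size is conditional. It is zero if no active-arm patient met a rescue criterion, and the documents give no rescue rate. Per affected patient who ends at no change, Step 4 is the upper figure for both endpoints, and a Week 26 value that already shows no benefit reduces it. These figures assume 16 evaluable patients per arm, the planned effects, a placebo mean of zero, and (for the reduced figures) assumed Week 26 means and correlations. A shift of this size from one patient is small against either planned effect. The reason to correct it is that the primary dataset should not depend on how an undefined term is read.

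**What to change.** In SAP 2.4.5 and 2.4.5.1, state: *Data after a placebo-to-olipudase alfa switch are excluded; data from olipudase alfa patients who meet a rescue criterion are kept through Week 52.* Use the same meaning wherever initiation of rescue therapy appears, including the post-Week 38 substitution, the Wilcoxon patient exclusion and the exposure definitions in 2.4.4.1.

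Protocol Appendix C gives 17 October 2019 as the cutoff at the end of the PAP, so the wording can now serve only as a documented clarification. The report should therefore state how many active-arm patients met a criterion and which reading was applied. If any of their later data were dropped, show the protocol-rule MMRM for DLco, spleen volume and platelets beside the reported result.

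The cost is a few sentences, one count from existing data and, only if data were dropped, one model rerun per endpoint. No new data or patients are needed. If the count is zero, one sentence in the report closes the matter.

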8.1.6 Rescue treatment

If during the course of the study, a patient satisfies one or more of the following criteria indicative of clinical decline due to ASMD progression and after excluding other possible causes, study drug will be unblinded and the patient will be switched to the 3.0 mg/kg olipudase alfa group; dose escalating procedures and caveats provided in [Table 1](#) and [Section 8.1.3](#) will apply. See the study manual and the IXRS manual for unblinding procedures.

- Hemoglobin level falls below 7 g/dL and remains below 7 g/dL when hematology laboratory testing is repeated after approximately 2 weeks.
- Platelet count falls below 30 000/mm³ and remains below 30 000/mm³ when hematology laboratory testing is repeated after approximately 2 weeks.
- A clinically significant bleeding episode assessed by the investigator as related to a low platelet count.

These patients will continue to be followed in the study. Upon confirmation of the need for rescue treatment, patients will have organ volume MRI and PFTs performed if prior tests were performed more than 12 weeks before.

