### 1.3 DETERMINATION OF SAMPLE SIZE

The sample size calculations are based on the 2 primary efficacy endpoints:

1. Percentage change in DLco (expressed as % predicted of normal) from baseline to Week 52
2. a) For Europe and the rest of the world (ROW) outside of USA: the percentage change in spleen volume (expressed in multiples of normal [MN] ) from baseline to Week 52  
  
b) For US: the combination spleen endpoint which consists of two components: the percentage change in spleen volume (expressed in MN) from baseline to Week 52 and change in splenomegaly-related score from baseline to Week 52.

Although the multiplicity adjustments in statistical testing of hypotheses ensures the study to be positive if only one of the two primary endpoints is significant ([Section 2.4.5.3](#)), each endpoint has been powered adequately in order to choose the sample size for the study as 36 randomized patients in 1:1 ratio in placebo and olipudase alfa treatment arms.

Endpoint	Null hypothesis	Assumptions			Signif. level	Sample Size N	Power
		Trt Diff	SD	Non-evaluable			
DLco	There is no difference between olipudase alfa group and placebo group in percentage change from baseline in percent predicted DLco from baseline to Week 52.	25%	20%	11%	0.05	36	0.93
Spleen Volume	There is no difference between olipudase alfa group and placebo group in percentage change from baseline in spleen volume in multiples of normal from baseline to Week 52.	30%	11.8%	11%	0.05	36	0.99
SRS	There is no difference between olipudase alfa group and placebo group in change from baseline in SRS from baseline to Week 52.	8	9.4	11%	0.15	36	0.82

The following assumptions for the DLco endpoint are based on results obtained from the olipudase alfa Phase 1b study DFI13412:

- A 20% common standard deviation
- A 25% mean difference from baseline to Week 52 between olipudase alfa and placebo in percentage change in DLco (in % predicted)
- An expected exclusion rate from the primary analysis due to non-availability of results at Week 52 is 11%

Based on these assumptions, a comparison between the olipudase alfa arm and the placebo arm will have 93% power using a t-test at a 2-sided 5% significance level and with 36 patients randomized 1:1 to placebo and olipudase alfa.

The assumptions for the spleen volume endpoint are the following:

- An 11.8% common standard deviation based on data from previous ASMD and Gaucher disease Type 1 studies

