#### **2.4.5.5 Responder analyses for the primary endpoints in PAP**

For the responder analyses specified below, binary measure of responder (yes vs no) at Week 52 will be analyzed with logistic regression including treatment and baseline as covariates. Patients who had missing data at Week 52 will be counted as non-responder. Number and % of responder, as well as odds ratio, 95% CI and p-value from the logistic regression model will be provided.

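### The Wilcoxon sensitivity analysis removes patients who start rescue therapy, while the SAP's general efficacy rule keeps them and drops only their post-rescue data

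*SAP*

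**What the plan says.** SAP 2.4.5.1 lists sensitivity analyses for the primary endpoints. The third is introduced with "The MMRM planned for the primary efficacy analysis assumes multivariate normality" and answers that assumption with a Wilcoxon-Mann-Whitney test, in which "missing Week 52 data will be imputed using LOCF, excluding patients who initiate rescue therapy". No value or rank is given for the excluded patients, and no reason for excluding them.

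The general rule in SAP 2.4.5, on efficacy analysis in the mITT population, is different: "This will include patients who used rescue therapy, but their data after rescue will NOT be included in the analysis". The second sensitivity analysis goes further and states that "the observations collected after the initiation of rescue therapy will be included in the MMRM", by randomized arm.

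Protocol 8.1.6 ties rescue to "criteria indicative of clinical decline due to ASMD progression", after other causes are excluded. The criteria are a confirmed hemoglobin below 7 g/dL, a confirmed platelet count below 30 000/mm³, or clinically significant bleeding attributed to a low platelet count. Once the need for rescue is confirmed, "patients will have organ volume MRI and PFTs performed if prior tests were performed more than 12 weeks before".

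**The concern.** Starting rescue happens after randomization and reflects disease progression. Removing people for that reason breaks the randomized comparison in an analysis offered as evidence of robustness. The direction depends on the arm. Losing decliners from the olipudase alfa arm flatters the drug, and losing them from placebo hides evidence in its favour.

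There is a second problem. The test is there to show whether the result depends on normality. Because it changes the analysed population as well as the method, a disagreement with the MMRM could not be put down to non-normality, and agreement would be less reassuring than it looks.

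**Working it through.** **1. Reproduce the plan's power.** Inputs are from SAP 1.3: 36 patients 1:1, 11% non-evaluable, DLco difference 25 and SD 20. Evaluable patients: 36 × 0.89 = 32.04, so 16 per arm. Noncentrality = 25 / (20 × √(2/16)) = 25 / 7.07 = 3.54 on 30 degrees of freedom. Two-sided power at 5% is 92.8%, matching the stated figure ("will have 93% power using a t-test at a 2-sided 5% significance level and with 36 patients randomized 1:1"). The same method gives over 99.9% for spleen volume (difference 30, SD 11.8; stated over 99%) and 82.3% for SRS (difference 8.0, SD 9.4, level 0.15; stated 82%).

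**2. Compare the rules for rescued patients.** SAP 2.4.5 keeps the patient and removes observations made after rescue. Sensitivity analysis 2 keeps the patient and the post-rescue observations. The Wilcoxon analysis, read plainly, removes the patient. On the narrower reading, where the clause limits only LOCF, a rescued patient is still lost unless a usable Week 52 value exists. One route to such a value is the SAP 2.4.5.1 rule that lets a PFT taken after the Week 38 infusion stand as Week 52.

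**3. Size of the effect.** The SAP gives no power for this test, so it was simulated: normal data, 18 per arm, DLco difference 25, SD 20, two-sided Mann-Whitney test at 5%. The number rescued (k, all in one arm) is an assumption, and so is whether rescue is related to DLco. Cells show the percentage of trials reaching significance.

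| Scenario | All kept | Dropped, k = 2 | Dropped, k = 3 |
|---|---|---|---|
| Rescued on olipudase alfa, lowest DLco in arm | 94 | 98 | 99 |
| Rescued on placebo, lowest DLco in arm | 94 | 87 | 81 |
| No true effect, lowest DLco in one arm | 5 | 9 | 14 |
| Rescue unrelated to DLco, either arm | 94 | 92–93 | 92 |
| No true effect, rescue unrelated to DLco | 5 | 4–5 | 4–5 |

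Monte Carlo error is up to about 1 point. With 16 per arm the pattern is the same. The no-rescue power is 91%. Dropping the 2 (3) lowest gives 97% (98%) if they are on olipudase alfa and 81% (72%) if on placebo.

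**4. Other endpoints, 16 per arm.** SRS at 0.15 has about 80% power with nobody rescued. Dropping the 1, 2 or 3 worst placebo patients gives 73, 64 or 55%. Spleen volume stays at about 100% when patients are dropped, because the assumed effect is about 2.5 SD (30 / 11.8).

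**The case against.** The strongest reply is that this is one sensitivity analysis with no alpha attached, and that rescue is handled elsewhere. The primary MMRM keeps pre-rescue data, sensitivity analysis 2 keeps post-rescue data, and in the responder analyses "Patients who had missing data at Week 52 will be counted as non-responder". SAP 2.2 also reports how many patients were rescued. All of that stands and sets the severity. SAP 2.4.5 allows exceptions to its population rule, so the clause is an unexplained departure and not a strict contradiction.

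A reader might infer that the exclusion discards the worst DLco, spleen or SRS values. The documents do not show this. Rescue is triggered by hemoglobin, platelets or bleeding, so these patients are worse in clinical course but not demonstrably worse on the endpoints.

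A reader might also infer that rescued patients must be placed at worst rank, and measure the harm by that yardstick. With 2 (3) olipudase alfa rescues unrelated to DLco, dropping gives about 92% (92%) and worst rank about 69% (43%). Those gaps do not measure bias from dropping. Under that assumption the dropped patients are a random subset and the test holds its level. The fall comes from moving typical responders to the bottom. If the rescued patients really are lowest on DLco, worst rank gives about 90% (82%), and the distortion is that dropping rises to 98% (99%). Worst rank also turns the analysis into a composite, which again mixes a change of question with the check on normality.

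**Conclusion.** The point holds as a low-severity defect. As written, the Wilcoxon analysis loses some or all rescued patients after randomization, for a reason linked to decline, and departs from the SAP's own general rule without explanation.

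The effect on DLco ranges from negligible to material. Dropping costs 1 to 3 points, with no bias, if rescue is unrelated to DLco. If the 2 or 3 rescued patients are the lowest in their arm, power shifts by roughly +4 to −13 points (94% to 98–99%, or to 87–81%), and the false-positive rate rises to about 9–14%. Both the rescue counts and the link to DLco are assumptions. If nobody is rescued, nothing changes. Spleen volume is essentially unaffected. No formal conclusion in SAP 2.4.5.3 depends on this test.

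**What to change.** Reword sensitivity analysis 3 so that rescued patients stay in the Wilcoxon test by randomized arm, with their last pre-rescue value used as the Week 52 value. That value includes the MRI and PFTs that Protocol 8.1.6 calls for when rescue is confirmed, provided they precede the first rescue infusion. This matches SAP 2.4.5 and leaves the test addressing distribution alone. State that patients rescued before any post-baseline measurement enter with zero change. Report the number rescued by arm beside the result.

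Optionally add a worst-rank version, same rule in both arms, labelled as a composite of rescue and Week 52 value.

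The cost is a sentence or two of SAP text and a few lines of code. The downside is that LOCF is applied to a few more patients, and for SRS the carried value may be older, since Protocol 8.1.6 asks for no eDiary at rescue. The rule belongs in the SAP before the primary-period unblinding. If that has already happened, run the retained version alongside and label it as added afterwards.
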